4.5 Maternal Exclusion Criteria, Cohort 2 M-I pairs enrolled after delivery

4.51 Receipt of disallowed medications within 4 weeks prior to delivery (See Section 4.8).

4.6 Infant Inclusion Criteria, Cohort 2 M-I pairs enrolled after delivery

4.61. Infant birth weight \leq 2500 grams.

4.62. Infant \leq 48 hours of age.

4.7 Infant Exclusion Criteria, Cohort 2 M-I pairs enrolled after delivery

4.71. Received disallowed medications described in Section 4.8.

Note: If any of the disallowed medications are required for the infant's care after enrollment, the infant will be ineligible for further PK sampling. Data will be obtained up to the time of the introduction of the disallowed medication, but such infant will not be considered one of the evaluable 15 infants if fewer than 3 PK samples from the first 5 time points are collected.

4.72 Infant has a severe congenital malformation or other medical condition not compatible with life or that would interfere with study participation or interpretation, as judged by the examining clinician.

4.8 Disallowed Medications

Raltegravir is eliminated mainly via a UDP glucuronosyltransferase UGT1A1-mediated glucuronidation pathway and may be subject to drug-drug interactions when co-administered with drugs that are known to be UGT1A1 inducers or inhibitors. However, raltegravir is not anticipated to affect the metabolic clearance of drugs metabolized by UGT1A1 given its low UGT1A1 inhibitory (IC_{50} for the inhibition of UGT1A1 $>50 \mu M$) and induction potential. Since raltegravir is neither an inducer nor inhibitor of cytochrome P-450 enzymes, raltegravir is not expected to result in metabolic drug interactions with substrates of cytochrome P-450.

The following medications/therapies are not permitted within 4 weeks prior to enrollment in women because these medications are potent broad inducers of drug metabolism and have been demonstrated to cross the human placenta. Their use with raltegravir may result in increased metabolism of raltegravir and lower raltegravir exposure in both mother and fetus: 1) phenobarbital; 2) phenytoin; 3) rifampin.

4.9 Enrollment Procedures

Prior to implementation of this protocol, and any subsequent full version amendments, each site must have the protocol and the protocol informed consent form(s) approved, as appropriate, by their local institutional review board (IRB)/ethics committee (EC) and any other applicable regulatory entity (RE). Upon receiving final approval, sites will submit all required protocol registration documents to the DAIDS Protocol Registration Office (DAIDS PRO) at the Regulatory Support Center (RSC). The DAIDS PRO will review the submitted protocol registration packet to ensure that all of the required documents have been received.

Site-specific informed consent forms (ICFs) WILL be reviewed and approved by the DAIDS PRO and sites will receive an Initial Registration Notification from the DAIDS PRO that indicates successful completion of the protocol registration process. A copy of the Initial Registration Notification should be retained in the site's regulatory files.

Upon receiving final IRB/EC and any other applicable RE approval(s) for an amendment, sites should implement the amendment immediately. Sites

are required to submit an amendment registration packet to the DAIDS PRO at the RSC. The DAIDS PRO will review the submitted protocol registration packet to ensure that all the required documents have been received. Site-specific ICF(s) *WILL NOT* be reviewed and approved by the DAIDS PRO and sites will receive an Amendment Registration Notification when the DAIDS PRO receives a complete registration packet. A copy of the Amendment Registration Notification should be retained in the site's regulatory files.

For additional information on the protocol registration process and specific documents required for initial and amendment registrations, refer to the current version of the DAIDS Protocol Registration Manual.

Enrollment of participants onto the study will be done through the Subject Enrollment System (SES) on the DMC website (at <https://www.fstrf.org>) under the Systems heading.

If a potential P1097 woman who signs informed consent for herself and her infant does not meet the eligibility criteria as outlined in Section 4.0, or the woman withdraws consent prior to enrollment, the site **MUST** notify the protocol team. This communication should include the reason the woman or infant was ineligible or if the woman withdrew consent. Data on reasons why the woman or infant is ineligible will be collected in the DMC database. This information may be used by Merck & Co., Inc. when reporting to Regulatory Agencies.

4.10 Co-enrollment Procedures

Co-enrollment in the raltegravir arms of P1026S and P1081 will be allowed. Co-enrollment in other research protocols will require the consent of the protocol chair of P1097 and the other research protocol.

5.0 STUDY TREATMENT

No treatment or intervention will be provided as part of this study. Infants will receive standard of care antiretroviral therapy for PMTCT as prescribed by their primary care physicians. HIV-infected pregnant women will be receiving raltegravir as prescribed by their care provider as part of a regimen for treatment of maternal HIV disease and/or prevention of mother to child transmission of HIV.

6.0 SUBJECT MANAGEMENT

6.1 Toxicity Management

This study does not contain any study-specific treatment or intervention, thus there is no need for toxicity management through the DAERS system. However, safety data will be collected and reviewed by the study team on regular team conference calls.

6.2 Permanent Study Discontinuation

The woman and/or infant will be discontinued from the study for the following reasons:

- The woman and/or infant is lost to follow up.
- The woman and/or infant is not able to attend study visits as required by the study.
- The subject/parent/guardian withdraws consent.
- The investigator determines that further participation would be detrimental to the woman's or infant's health or well-being.

The study may be discontinued at any time by the IMPAACT network, the Office for Human Research Protections (OHRP), the National Institutes of Health (NIH), the local IRB or EC, U.S. Food and Drug Administration (FDA), the pharmaceutical sponsor, or other governmental agencies.

6.3 Premature Discontinuation/Early Withdrawal/Safety Follow-up for PK Unevaluable Infants

Cohort 1 (Closed): If the infant is not eligible for pharmacokinetic sampling, study evaluations will be performed for safety monitoring between 8-14 hours after birth, 30-36 hours after birth, week 1-2 and week 20. If the parent withdraws consent at any time after enrollment, no further information will be collected and additional laboratory evaluations will not be performed.

Cohort 2: If fewer than 3 pharmacokinetic samples from the first 5 time points are collected, the infant is not considered evaluable for pharmacokinetics but will continue with scheduled safety evaluations. If the parent withdraws consent at any time after enrollment, no further information will be collected and additional laboratory evaluations will not be performed.

7.0 EXPEDITED ADVERSE EVENT REPORTING

This study does not contain any study-specific treatment or intervention, thus no expedited adverse event (EAE) reporting is required. Every effort will be made by study staff to provide appropriate care and counseling to the participant, and/or referral to appropriate resources for the safety of the participant as needed. Any unanticipated problems will be reported to the DAIDS Medical Officer at the

same time as the problems are reported to the responsible site IRB/Ethics Committees (ECs) overseeing the research according to pre-established procedures as required by 45 CFR 46.

8.0 STATISTICAL CONSIDERATIONS

8.1 General Design Issues

This is a multi-center pilot trial to estimate washout pharmacokinetics and safety of raltegravir in infants born to HIV-infected pregnant women receiving raltegravir prior to delivery and continuing during labor. Results of the washout pharmacokinetics will be used to develop an initial neonatal dosing regimen of raltegravir to be evaluated in a follow-up study.

There are two cohorts:

- **Cohort 1 (fully accrued and follow up complete): M-I pairs were enrolled prior to delivery (at \geq 35 weeks gestation); and**
- **Cohort 2: This cohort will enroll low birth weight infants (weight \leq 2500 grams at birth) prior to delivery or within 48 hours after delivery.**

The protocol was amended to Version 2.0 to enroll low birth weight (\leq 2500 grams) infants in Cohort 2. Cohort 2 will accrue mother-infant (M-I) pairs until 15 evaluable infants have been enrolled for the washout pharmacokinetic analysis.

No study-specific treatment will be given to mother or infant during this study. Washout pharmacokinetic data and analyses are described in detail in Section 9.0. Safety data will include adverse birth outcomes and infant adverse events observed during follow-up. **Cohort 1 safety data will be analyzed separately from Cohort 2 safety data.**

This is a pilot study and the sample size has been determined by the protocol pharmacologist to provide enough information needed to develop an initial LBW neonatal dosing regimen for a follow-up study (IMPAACT P1110). The safety analysis will include the data on all enrolled infants, including infants who were not evaluable for the washout pharmacokinetic analysis. The study is not powered for the analysis of the safety data. Descriptive statistics will be generated to summarize the safety data.

Unless otherwise indicated, the rest of the subsections below refer to both Cohorts 1 and 2.

8.2 Outcome Measures

8.21 Primary Outcome Measures:

Pharmacokinetic Outcome Measures:

- Neonatal raltegravir elimination ($t_{1/2}$). See Section 9.0.
- Raltegravir maternal-cord blood ratio. See Section 9.0 **for Cohort 1 only**

Note: Cord blood and maternal delivery plasma samples will not be collected from Cohort 2 M-I pairs who enroll after delivery.

Safety Outcome Measures:

- Infant adverse events of Grade 3 or 4 as defined in DAIDS Table for Grading the Severity of Adult and Pediatric Adverse Events (DAIDS AE Grading Table), Version 1.0, dated December 2004, Clarification August 2009, which is available on the RSC website at <http://rsc.tech-res.com/safetyandpharmacovigilance>
 - Adverse birth outcomes including stillbirth and low birth weight **(for Cohort 1 only)**
 - Infant death
 - Total bilirubin
 - Direct bilirubin

For Cohort 1, occurrence of infant adverse events of Grades 3 or 4 adverse birth outcomes, and infant death will constitute the infant meeting a toxicity endpoint. For Cohort 2, occurrence of infant adverse events of Grades 3 or 4 and infant death will constitute the infant meeting a toxicity endpoint. **As part of the secondary safety analysis for Cohorts 1 and 2, (i) information on number and proportion of infants requiring therapy (e.g. phototherapy, exchange transfusion) to reduce bilirubin and (ii) summary statistics for total and direct bilirubin will be provided.**

8.22 Secondary Outcome Measures:

Pharmacokinetic Outcome Measures:

- Optional genotyping for polymorphism of UGT1A1 from infants who are eligible for pharmacokinetic sampling as described in Section 9.0.

8.3 Randomization and Stratification

There will be no randomization and no stratification.

For Cohort 1, because of the potential for a drug interaction between atazanavir and raltegravir, the number of women enrolled receiving an atazanavir-containing regimen **was** limited to three. **This restriction has been removed for Cohort 2.**

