ATV/RTV ‡§	↑ 77%	↑ 41%	↑ 24%
Ritonavir (RTV) ‡	↓ 1%	↓ 16%	↓ 24%
Efavirenz ‡	↓ 21%	↓ 36%	↓ 36%
Tipranavir/RTV ‡§	↓ 55%	↓ 24%	↓ 18%
Rifampin (400 mg RAL) ‡	↓ 61%	↓ 40%	↓ 38%
Rifampin (800 mg RAL) §	↓ 53%	↑ 27%	↓ 62%
Tenofovir ‡§	↑ 3%	↑ 49%	↑ 64%
Etravirine	↓34%	↓10%	↓11%

† AUC_{0-∞} for SD raltegravir ; AUC_{0-12h} for MD raltegravir
 ‡ Multiple doses of concomitant medication plus single dose (SD) of raltegravir
 § Multiple doses of concomitant medication plus multiple doses (MD) of raltegravir
 || 800 mg BID raltegravir + 600 mg QD rifampin compared to 400 mg BID raltegravir alone.

In summary, drug interaction studies to date have investigated the effects of strong inducers and inhibitors on raltegravir metabolism, and it is anticipated that these data would bracket the effects of other more modest inhibitors or inducers. In particular, the impact on raltegravir of atazanavir (a UGT1A1 inhibitor) is modest and that of rifampin (a strong inducer) is clinically manageable. Additionally, raltegravir was shown not to be an inducer or inhibitor of CYP3A4, as demonstrated in the midazolam interaction study, suggesting that raltegravir will not impact the pharmacokinetics of drugs metabolized by CYP3A4.

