1.25 Special Concerns for the use of Raltegravir in the Neonate

UGT1A1, the enzyme primarily responsible for raltegravir metabolism, is also the only enzyme that contributes to bilirubin glucuronidation in human hepatocytes, and as such is essential for the biliary elimination of bilirubin from the body [33].

Glucuronidation activity is low in fetuses and in the newborn immediately after birth but increases exponentially over the first weeks and months of life. Hepatic UGT activity in liver samples is very low in samples from 2nd trimester fetuses, and increases roughly 10 fold during the 3rd trimester and then another 100-fold during the first 3 months following a full term delivery [34]. The low level of hepatic UGT activity at birth plays a major role in the elevations of bilirubin routinely seen in the newborn, referred to as physiologic jaundice.

In adults, decreased UGT1A1 activity has been shown to result in increased plasma concentrations of both bilirubin and raltegravir. Atazanavir, an HIV protease inhibitor, is also an inhibitor of UGT1A1 and elevation of direct bilirubin is a very common side effect of atazanavir use in HIV infected adults. When raltegravir and atazanavir are co-administered, raltegravir AUC increases on average by 41% and C_{max} by 77% [22]. Similarly, the UGT1A1 *28/*28 genotype, one of the common genotypes found in individuals with Gilbert's Syndrome, is characterized by a roughly 30% decrease in UGT1A1 activity and increased serum bilirubin concentrations [35,36]. Following standard dosing with raltegravir, individuals with the UGT1A1 *28/*28 genotype have on average an increase of 40% in raltegravir AUC and C_{max} and of 90% in trough concentration compared to individuals with wild type UGT1A1. Raltegravir elimination t_{1/2} was not prolonged in the UGT1A1 *28/*28 individuals, suggesting that increased raltegravir bioavailability due to decreased hepatic first pass metabolism may play a major role in the increase in raltegravir plasma concentrations seen in these individuals [23].

Administration of an exogenous drug that is eliminated by glucuronidation poses special risks in the newborn. Low UGT

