1.26 Results of Cohort 1 Full Term Neonates Enrolled in P1097, Version 1.0

[figure not shown]
IMPAACT P1097, Version 1.0, *Raltegravir Pharmacokinetics and Safety in Neonates*, enrolled 22 mother-infant pairs: 59% of infants were African-American, 32% were white. Evaluable PK data were obtained from 19 mother-infant pairs. Median (range) PK parameters are listed below:

- Maternal delivery raltegravir concentration: 540 ng/mL (12-5809 ng/mL) or 1.22 µM (12-13.07 µM)
- Cord blood raltegravir concentration: 957 ng/mL (24-3974 ng/mL) or 2.15 µM (0.05-8.94 µM)
- Ratio of cord/maternal blood raltegravir concentration: 1.48 (0.32-4.33)
- Initial infant plasma raltegravir concentration: 671 ng/mL (13-2672 ng/mL) or 1.51 µM (0.03-6.01 µM)
- Infant plasma raltegravir concentration at 30-36 hours: 291 ng/mL (BLQ-1402 ng/mL) or 0.65 µM (BLQ-3.15 µM)
- Median infant apparent t ½ of raltegravir concentration: 26.6 (9.3-184) hours

Infant washout raltegravir concentrations initially increased before decreasing in 9 of 18 evaluable infants. All infants tolerated RAL exposure well with 20-week follow-up evaluations completed in all infants with no unexpected adverse events and no transmission of HIV infection.

From this study it was determined that raltegravir readily crosses the placenta. The plasma $t_{1/2}$ of raltegravir in neonates is highly variable suggesting potential roles for developmental aspects of neonatal UGT1A1 enzyme activity, redistribution and/or enterohepatic recirculation of raltegravir. Understanding the features of raltegravir PK in full-term and low birth weight neonates will be critical for development of a neonatal dosing regimen (see Figure 1).

Figure 1: Infant RAL Concentration-Time (hours) Plot (P1097, Version 1.0).

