- **Infant not receiving disallowed medications described in Section 4.8. If these medications are required for the infant's care, the infant will be ineligible for further PK (pharmacokinetic) sampling. Data will be obtained up to the time of the introduction of the disallowed medication, but such infant will not be considered one of the evaluable 15 infants.**
- **Infant \leq 48 hours of age.**

Blood samples for raltegravir assay will be collected at 1-6, 12-24, 36-48, 72-84, and 108-132 hours after birth, and on day 7-14. Infants may enroll up to 48 hours of age, and any pharmacokinetic samples scheduled for collection prior to the time of enrollment will be skipped and not replaced. Infants enrolling close to the 48-hour time point should have the first pharmacokinetic blood sample collected within 4 hours of enrollment (i.e., within 52 hours after birth) so that a minimum of three blood samples can be obtained for pharmacokinetic evaluation.

With regard to infant blood samples for safety/toxicity laboratory testing: In the event that the study-required study safety/lab samples have not been collected prior to enrollment, (e.g., due to infant enrolled after delivery), these must be collected as soon as possible after enrollment. To meet the primary objectives of the study, only those infants who have at least 3 pharmacokinetic blood samples collected from the first 5 time points will be considered to be evaluable.

Optional genotyping for polymorphisms of UGT1A1 **were performed on Cohort 1 infants and** will be performed **on Cohort 2** infants who undergo pharmacokinetic sampling. **The goal of the genotypic analysis** is to determine if certain polymorphisms, particularly those with the UGT1A1*28/*28 genotype have slower RAL elimination than those with the UGT1A1*1/*1 genotype. Because UGT1A1 activity is reduced in neonates, polymorphisms associated with reduced activity are likely to have a larger impact on the metabolism of raltegravir, especially those who are low birth weight.

No study-specific drugs will be given to women or infants during this study. Women will be receiving raltegravir for clinical indications outside of the study. Infants will receive standard of care antiretroviral therapy for prevention of mother-to-child transmission (PMTCT) as prescribed by their primary care physicians.

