APPENDIX I-B

COHORT 2 MATERNAL SCHEDULE OF EVALUATIONS

	Screening/entry	Labor/delivery ⁶	Post-Delivery (1-5 days after delivery)
Informed Consent	X		
CLINICAL EVALUATIONS			
History	X ¹	X ²	X ²
PHARMACOKINETICS⁷			
Maternal RAL concentration ³	1mL ⁴ If enrolled after delivery	1mL ⁴ If enrolled before delivery	
OTHER ⁷			
Cord Blood ^{3,5}		X	
TOTAL BLOOD	1mL	1mL	0mL

1. History data at Screening/entry includes documentation of HIV-1 infection, demographic data and antiretroviral dosing history 3 months prior to entry.
2. History data after Screening/entry includes antiretroviral dosing while on study, labor and delivery record, and obstetrical gestational age. It is strongly recommended that the site report, prospectively if possible, the mother to the Antiretroviral Pregnancy Registry (<http://www.apregistry.com/reg.htm>):
 US/Canada [contact], [contact]
 Brazil: [contact]
 International: [contact], [contact]
 Email: [contact]
3. Mother/infant pairs may be enrolled up to 48 hours after delivery. In these situations it may not be possible to collect the maternal and cord blood samples at labor and delivery.
4. For women enrolled prior to delivery, collect 1mL of maternal blood within one hour after delivery. For women enrolled after delivery, collect 1mL of maternal blood at the time of enrollment.
5. Draw cord blood immediately after cord is clamped.
6. Not applicable to women enrolled after delivery.
7. See the Laboratory Processing Chart (LPC) on the P1097 Protocol Specific Webpage on the IMPAACT website (<http://www.impaactgroup.org>) for collection, processing and shipping instructions.

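### Does lifting the Cohort 1 cap on atazanavir-treated mothers mean the plan must analyse Cohort 2 by maternal atazanavir use?

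*Protocol*

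**What the plan says.** Protocol Section 8.3 provides for no stratification. It explains the Cohort 1 limit of three women by a possible interaction ("because of the potential for a drug interaction between atazanavir and raltegravir") and then lifts it: "This restriction has been removed for Cohort 2". No reason for the removal is given there. Section 4.8 disallows only "1) phenobarbital; 2) phenytoin; 3) rifampin".

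On the interaction itself, Section 1.22 states that "the impact on raltegravir of atazanavir (a UGT1A1 inhibitor) is modest" and that the rise in raltegravir levels does not call for a dose adjustment. Section 1.25 adds that UGT1A1 is the main route of raltegravir metabolism and the only enzyme that glucuronidates bilirubin, and that raised bilirubin is very common in adults on atazanavir.

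The planned analyses are simple:

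- Protocol Section 9.3: regression for the terminal phase in each infant.
- Protocol Section 8.6 and SAP 3.3.1: bilirubin summaries by sampling time, and the proportion of infants needing bilirubin-lowering therapy.
- SAP 3.3.2: an unadjusted Wilcoxon comparison of half-life by genotype.

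None of them mentions maternal regimen, and the SAP does not mention atazanavir. The exposure is recorded, however: Appendix I-B, footnote 2, reads "History data after Screening/entry includes antiretroviral dosing while on study, labor and delivery record, and obstetrical gestational age".

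**The concern.** The study team itself singled out atazanavir, controlled it by design in Cohort 1, and then removed the control without naming a replacement in the analysis. The exposure bears on two primary outcomes (half-life and bilirubin) and on the secondary genotype objective, because all three run through the same enzyme. If many Cohort 2 mothers took atazanavir, a long half-life or a high bilirubin might partly reflect atazanavir rather than immaturity or raltegravir. The half-life feeds an initial dosing regimen for low birth weight infants whose mothers may not have taken it. In the genotype comparison, a chance imbalance in a handful of infants could look like a genotype effect.

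**Working it through.** The plan states no figure on this point, so there is none to reproduce. The check asks how large the effect could be and whether a breakdown would show it.

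**Inputs.** From the documents: 15 evaluable infants (Section 8.4); Cohort 1 half-life "26.6 (9.3-184) hours" (Section 1.26) with 19 evaluable infants; adult AUC ratios of 1.41 with boosted and 1.73 with unboosted atazanavir (Table 1, Section 1.22). Assumed, because the documents give no figure: exposed shares of 20%, 30% and 40%, and full carry-over of the adult AUC ratio to infant half-life.

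**1. Could exposure exceed the old limit?** Yes. With those shares, the binomial chance of more than three exposed among 15 is 35%, 70% and 91%.

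**2. Shift in the pooled geometric mean half-life** = ratio^share.

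| Ratio | 20% | 30% | 40% |
|---|---|---|---|
| 1.00 | 1.00 | 1.00 | 1.00 |
| 1.41 | 1.07 | 1.11 | 1.15 |
| 1.73 | 1.12 | 1.18 | 1.25 |

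**3. Sampling error.** Log-SD = ln(184/9.3) / 3.688, the divisor being the expected range of 19 standard normals: 2.985/3.688 = 0.81. The 90% confidence factor for n = 15 is exp(1.761 × 0.81/√15) = 1.44. To reach that factor, the exposed share would have to be ln(1.444)/ln(1.73) = 0.67 at ratio 1.73. At ratio 1.41 it would be ln(1.444)/ln(1.41) = 1.07, which is impossible.

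**4. How firm is the log-SD?** Not very. The Cohort 1 range is lopsided about its median. Scaling each side separately gives ln(184/26.6)/1.844 = 1.05 and ln(26.6/9.3)/1.844 = 0.57, so the factor for n = 15 runs from 1.61 down to 1.30. With the smallest SD, the share needed is 47% at ratio 1.73 and 75% at ratio 1.41. Every entry in the table above still lies below 1.30.

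**5. What leaving out exposed infants would do.** With 12 or 9 infants left, the factor becomes 1.52 or 1.65. For bilirubin-lowering therapy, taking 8 of 20 as an example, the exact 90% interval is 0.22 to 0.61; a restricted 5 of 12 gives 0.18 to 0.68. (The Section 8.4 table prints 0.19 to 0.64 for 40% of 20, which are the 95% limits.) A test of exposed against unexposed half-life, with 3 to 7 of 15 exposed and true ratios of 1.41 to 2.0, has simulated power of about 8% to 29%.

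**6. Genotype comparison.** Take a deliberately bad imbalance: 3 of 3 variant infants exposed against 3 of 12 others. The spurious half-life ratio is ratio^(1 − 0.25), that is 1.29 at 1.41 and 1.51 at 1.73. The 90% factor for comparing 3 with 12 infants is exp(1.771 × 0.81 × √(1/3 + 1/12)) = 2.52, well above either.

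**7. Is there a route to the infant's half-life?** There are two candidates. Atazanavir may raise the mother's raltegravir level; under first-order elimination that raises the infant's starting concentration and leaves the half-life unchanged. Or atazanavir may reach the infant and inhibit its own UGT1A1; the documents say nothing about placental passage or persistence of atazanavir. The nearest evidence is in adults with reduced UGT1A1 activity, whose half-life "was not prolonged in the UGT1A1 *28/*28 individuals, suggesting that increased raltegravir bioavailability due to decreased hepatic first pass metabolism" may largely explain their higher concentrations. These infants take no oral raltegravir.

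**The case for a change.** The best case for acting rests on bilirubin and on principle. The first-pass argument concerns raltegravir bioavailability and offers no reassurance about bilirubin, where the protocol reports a very common adult effect. Section 3.0 also expects that "polymorphisms associated with reduced activity are likely to have a larger impact on the metabolism of raltegravir, especially those who are low birth weight", so adult data may understate what inhibition does in this population. A bias smaller than the sampling error is still a bias and adds to it. The remedy is cheap, since maternal dosing is already recorded.

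Much of this stands. Maternal atazanavir is the obvious covariate to list, and a reader of the results would want to see it. But Section 3.0 speaks of polymorphisms, gives no size and does not mention atazanavir. For bilirubin the documents offer no neonatal figure at all, so an effect is possible but not shown. The claim that pooled results could not be attributed goes too far: infant-level data and maternal dosing records are both held, so exposed infants can be identified whenever a result calls for it. SAP Section 4 already lists baseline characteristics and leaves their content to the Analysis Implementation Plan, and SAP 1.1 leaves the pharmacokinetic data to the protocol pharmacologist. Either may already cover the point.

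**Conclusion.** The observation is correct as far as the protocol and SAP go, but it is a gap in descriptive detail, and the documents do not show that the plan as written gives a wrong or worse answer. The half-life effect may be zero. Under full carry-over of the adult AUC ratios and up to 40% exposure it is at most 25%, against a confidence factor of about 1.44 (1.30 to 1.61 depending on how the Cohort 1 spread is read). A restricted analysis would be less precise and would seldom differ detectably from the pooled one. This is a 15-infant pilot without hypothesis tests on safety, and its dosing regimen goes to a follow-up study for evaluation.

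The conclusion rests on the assumed exposure shares, on Cohort 1 variability applying to low birth weight infants, and on the adult AUC ratios as a plausible ceiling. That ceiling is not a strict bound: Section 1.22 quotes increases of up to about 100% across parameters, and a ratio of 2.0 at 40% exposure would give 2.0^0.4 = 1.32, still below 1.44 though just above 1.30. For bilirubin the size is unknown. Analysts can describe maternal atazanavir use from records already collected, with no amendment.
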